## Document History – Changes compared to previous final version of SAP

Date	Time point	Reason for update	Outcome for update	Section and title impacted (Current)
23-Jun-2016	Prior to DB lock	Final version created		

## List of abbreviations

ACR	American College of Rheumatology
AE	Adverse event
ALT/SGPT	Alanine aminotransferase/serum glutamic pyruvic transaminase
ANCOVA	Analysis of covariance
AS	Ankylosing Spondylitis
ASAS	Assessment of Spondyloarthritis International Society
AST/SGOT	Aspartate aminotransferase/serum glutamic oxaloacetic transaminase
axSpA	axial Spondyloarthritis
BASDAI	Bath ankylosing spondylitis disease activity index
CASPAR	Classification criteria for Psoriatic Arthritis
CRP	C-reactive protein
CSR	Clinical Study report
CTC	Common Toxicity Criteria
DMARD	Disease Modifying Anti-rheumatic Drug
DMC	Data Monitoring Committee
DS&E	Drug Safety & Epidemiology
ECG	Electrocardiogram
FAS	Full Analysis Set
eCRF	Electronic Case Report Form
hCG	human chorionic gonadotropin
hsCRP	High sensitivity C-Reactive Protein
IVR	Interactive Voice Response
IWR	Interactive Web Response
LEI	Leeds Enthesitis Index
LFT	Liver function test (raised serum transaminases and/or bilirubin levels)
MedDRA	Medical Dictionary for Drug Regulatory Affairs
MRI	Magnetic resonance imaging
MTX	Methotrexate
NRS	Numerical rating scale
PCS	Physical Component Summary
PFS	Prefilled syringe
PRO	Patient Reported Outcome
PsA	Psoriatic arthritis
PsAMRIS	Psoriatic Arthritis Magnetic Resonance Imaging Score
RA	Rheumatoid arthritis
RF	Rheumatoid factor
SAE	Serious adverse event
SAP	Statistical Analysis Plan
s.c.	Subcutaneous(ly)
SF-36	Medical Outcome Short Form (36) Health Survey

---

SJC	Swollen Joint Count
SmPC	Summary of Product Characteristics
SpA	Spondyloarthritis
SUSAR	Suspected Unexpected Serious Adverse Reactions
TJC	Tender Joint Count
TNF	Tumor necrosis factor
ULN	Upper limit of normal
VAS	Visual analog scale
WBC	White blood cell
WHO	World Health Organization

## 1 Introduction

This SAP module describes the planned statistical methods for all safety and efficacy analyses. Any changes made to the statistical plan and methodology after the clinical database lock will be documented as an addendum.

The main purpose of this document is to provide summary of the statistical methodology that will be used for this clinical study; this includes a detailed description of data summaries. Analyses plan in this document refers to the related statistical analysis sections in clinical study report.

Data will be analyzed by Novartis according to the data analysis section 9 of the clinical study protocol. That statistical methodology is described below and any deviations from the protocol are documented. Additional detailed information regarding the analysis methodology is contained in the Appendix section.

This SAP describes the planned statistical methods. It is structured as

- A draft of the Clinical Study Report (CSR) Section 9.7 (statistical methods planned in the protocol and determination of sample size) and
- A draft of CSR Appendix 16.1.9 (documentation of statistical methods). Appendix 16.1.9 text will contain details of statistical methods and issues that are too long to include in the CSR text.

Please refer to the following document:

[figure not shown]
- Clinical Protocol CAIN457F3301

### 1.1 Study design

This is a 52-week, randomized, parallel-group, double-blind, multicenter, international study consisting of an 8-week screening period, a 24-week, placebo-controlled, double-blind treatment period and a 28-week open-label treatment period in patients with PsA and axSpA.

The dosing of secukinumab will be applied according to the approved European Summary of Product Characteristics (SmPC) in PsA and AS disease. According to SmPC, patients with AS and PsA (with concomitant none-to-mild psoriasis) will receive 150 mg secukinumab or placebo (1 PFS) where as only PsA patients with concomitant moderate-to-severe-psoriasis will receive 300 mg of secukinumab or placebo (2 PFS). In case of axSpA patients with objective signs of inflammation at screening, evident by either MRI with Sacroiliac joint inflammation (according to source documentation) and/or hsCRP > upper limit of normal (ULN, as defined by central lab) , secukinumab/placebo will be applied as 1 (1.0 mL pre-filled syringe (PFS) of 150 mg dose) s.c. injection.

The study design is given in Figure 1.

**Figure 1: Study design****Planned number of patients and randomization**

At Baseline approximately 200 patients will be randomized. Randomization will occur to one of the following two treatment groups in a ratio of 1:1.

- Group 1 (secukinumab): secukinumab as 1 (1.0 mL pre-filled syringe (PFS) of 150 mg dose) s.c. or 2 (2 x 1.0 mL PFS of 150 mg dose, 300 mg) s.c. injections according to axSpA or PsA disease at Baseline, Weeks 1, 2, and 3, followed by administration every 4 weeks starting at Week 4.
- Group 2 (placebo): placebo as 1 (1.0 mL PFS) or 2 (2 x 1.0 mL PFS) s.c. injections according to axSpA or PsA disease at Baseline, Weeks 1, 2, 3, followed by administration every 4 weeks starting at Week 4.

Patients will receive study treatment at Baseline, Weeks 1, 2, and 3, followed by treatment every 4 weeks through Week 52 (last dose given at Week 48). At Week 24, patients originally randomized to placebo will switch to receive secukinumab 150 mg (1 injection of secukinumab 1 mL/150 mg) or secukinumab 300 mg (2 injections of secukinumab 1 mL/150 mg) in open-label fashion without a loading regimen.

Blinding to the original treatment assignment will be maintained until after the Week 52 database lock and analyses are completed. However, original randomized treatment assignment to secukinumab or placebo will remain double-blinded to all patients, investigators, and site personnel, whereas the Sponsor (including the Region Europe Clinical Team, statisticians and data management) will be unblinded after the Week 24 database lock (protocol [Section 3.5](#)) and analyses are completed (protocol [Section 9.7](#)).

Patients will be stratified at randomization on the basis of PsA or axSpA disease.

Based on enrollment target, it is planned that approximately 50% of randomized patients should be PsA and approximately 50% axSpA patients to ensure a balanced patient population for the assessment of efficacy and safety.

### **Primary analysis time point**

The primary analyses will be performed at Week 24.

### **Interim analyses**

No interim analysis is planned for this study.

Once all data until/including Week 24 (containing the primary and secondary endpoints) are complete and clean, the database for that study period will be locked and analyzed. The results may be published or made available to personnel involved in data collection of this study prior to database lock of the complete study period until Week 52.

[figure not shown]
## **1.2 Study objectives and endpoints**

[figure not shown]
The following objectives will be evaluated in patients with active PsA and axSpA.

**Table 1.2-1 Objectives and related endpoints**

Objective	Endpoint
Primary objective	
To demonstrate the superiority of secukinumab to placebo based on the respective subcomponent of LEI at 24 weeks in patients with active PsA and axSpA	Percentage of patients with resolution of Achilles tendon enthesitis as assessed by the respective subcomponent of the LEI at 24 weeks
Secondary objectives	
To demonstrate the superiority of secukinumab to placebo at Week 24 based on the 10-point NRS	Mean change from baseline of heel pain measured on the 10-point NRS at Week 24
To demonstrate the superiority of secukinumab to placebo at Week 24 based on the respective subcomponent of PsAMRIS	Percentage of patients with an improvement of bone marrow oedema in the insertion of the Achilles tendon in the upper part of the calcaneus and/or in the insertion of the plantar aponeurosis in the lower part of the calcaneus as assessed by the respective subcomponent of the PsAMRIS at Week 24 in the affected foot at Baseline
To demonstrate the superiority of secukinumab to placebo at Week 24 based on the LEI	Percentage of patients with resolution of enthesitis as assessed by the LEI at Week 24

To demonstrate the superiority of secukinumab to placebo at Week 24 based on the physician's global assessment of disease activity	Mean change from baseline in physician's global assessment of disease activity at Week 24
To demonstrate the superiority of secukinumab to placebo at Week 24 based on the patient's global assessment of disease activity	Mean change from baseline in patient's global assessment of disease activity at Week 24
To demonstrate the superiority of secukinumab to placebo at Week 24 based on physician's global assessment of heel enthesiopathy	Mean change from baseline in physician's global assessment of heel enthesiopathy activity at Week 24
To demonstrate the superiority of secukinumab to placebo at Week 24 based on patient's global assessment of heel enthesiopathy	Mean change from baseline in patient's global assessment of heel enthesiopathy activity at Week 24
To demonstrate the improvement in secukinumab to placebo at Week 24 based on SF-36 PCS or SF-36v2	Change from Baseline in SF-36 PCS or SF-36v2
To describe the improvement in resolution of Achilles tendon enthesitis after switching from placebo to secukinumab at Week 24.	Percentage of patients with resolution of Achilles tendon enthesitis in patients switching from placebo to secukinumab at Week 24.
To demonstrate the improvement of heel pain after switching from placebo to secukinumab at Week 24.	Mean change of heel pain in patients switching from placebo to secukinumab at Week 24
The overall safety and tolerability of secukinumab	Overall safety, as measured by frequency and severity of adverse events and changes in laboratory, vital signs and ECG values from baseline

## 2 Statistical methods

### 2.1 Data analysis general information

The analysis will be conducted by Novartis on all patient data after database lock for the respective trial periods. Any data analysis carried out independently by the investigator should be submitted to Novartis before publication or presentation.

Analysis datasets and statistical outputs will be produced using the most recent SAS® Version 9.4 (SAS Institute Inc., Cary, NC, USA), and stored in Novartis global programming & statistical environment (GPS).

Following the Week 24 database lock, the Sponsor will be unblinded to treatment assignment. Once all data until/including Week 24 (containing the primary and secondary endpoints) are complete and clean, the database for that study period may be locked and analyzed.

Continuous variables will be summarized by number of patients, mean, standard deviation, minimum, median and maximum. Categorical variables will be summarized by absolute and relative frequencies. Summary statistics will also be presented graphically wherever applicable.

If not otherwise specified, p-values and confidence intervals will be two-sided. Unless otherwise stated, the level of significance will be set to 5% (two-sided, family-wise type-I-error).

#### 2.1.1 General definitions

**Study treatment:** Study treatment refers to:

Secukinumab 150 mg provided in 1 ml PFS or Secukinumab placebo provided in 1 ml PFS.

**Study treatment start and end date:** Study treatment start date is defined as the first date when a non-zero dose of study drug is administered and recorded on the Drug Administration Record (DAR) CRF page. Similarly, study drug end date is defined as the last date when a non-zero dose of study drug is administered and recorded on the DAR CRF page of the core study.

**Study day:** Study day will be calculated as (event date – study drug start date + 1 day) for events that occurred on or after study drug start date (e.g.visit, lab samples, AEs). For events prior to study drug start date (e.g., time of diagnosis), study day will be negative and calculated as (event date – study drug start date). Note that study drug start date is study day 1 and the day before study drug start date is study day -1 (i.e. no study day 0).

Due to the study drug dosing schedule, one month will be considered as 28 days. However, for “time since event” data (e.g., medical history), one month will be considered as 365.25/12 days for events that occurred prior to study Day 1. Time from events prior to the start of study drug, e.g., time since diagnosis, is calculated as the difference between the start date of study drug and the date of prior event.

Note that, the first dose day is Day 1, and the day before the first dose day is counted as Day -1 (not Day 0).

**Baseline and post baseline:** In general, a *baseline* value refers to the last measurement made prior to administration of the first dose of study treatment. A post-baseline value refers to a measurement taken after the first dose of study treatment.

**Treatment Period:** There are two treatment periods for this study defined as :

Treatment Period 1 is defined as a 24 Week placebo-controlled, double-blind treatment period starting from baseline till Week 24.

Treatment Period 2 is a 28 Week open-label treatment period starting from Week 28 (end of Week 24) till Week 52.

**Lost to follow up:** The patients whose study completion status is unclear because they fail to appear for study visits without stating an intention to withdraw.

**On-treatment period:** The period where the patients are exposed to the study treatment. For this study the treatment phase consists of 52 weeks (for treatment group 1) for secukinumab, and 24 weeks of on-treatment period for placebo and 28 weeks of on treatment for secukinumab (for treatment group 2).

## 2.2 Analysis sets

The following analysis sets will be used in this trial:

**Randomized set:** The randomized set will be defined as all patients who were randomized. Unless otherwise specified, miss-randomized patients (miss-randomized in IRT) will be excluded from the randomized set.

Mis-randomized subjects are defined as those subjects who were mistakenly randomized into the IVR prior to the site confirming all eligibility criteria had been met and to whom no study medication was given.

**Full analysis set (FAS):** The FAS will be comprised of all patients from the randomized set to whom study treatment has been assigned. Following the intent-to-treat principle, patients will be evaluated according to the treatment assigned to at randomization. For patients randomized erroneously into the wrong stratum, the actual stratum will be used for analyses.

**Safety set:** The safety set includes all patients who took at least one dose of study treatment during the treatment period. Patients will be evaluated according to treatment received.

### **2.2.1 Subgroup of interest**

The main subgroup of interest for this study are the PsA set of patients and axSpA set of patients. The two subgroups of PsA and axPsA patients will consist of approximately 50% in each of the total study population.

All (baseline, efficacy and safety) summaries will be performed based on this subgroup and overall.

A possible effect modification of patient characteristics will be explored by subgroup analyses for sex, age class and disease severity at Baseline.

## **2.3 Patient disposition, demographics and other baseline characteristics**

Summary statistics will be presented for continuous demographic and baseline characteristics for each treatment group and for all patients in the randomized set. The number and percentage of patients in each category will be presented for categorical variables for each treatment group and for all patients.

### **2.3.1 Patient disposition**

The number and percentage of patients who are screened will be presented. In addition, the reasons for screen failures will be provided.

The number and percentage of patients who are enrolled, and who completed each treatment period and who discontinued the study will be summarized by treatment group at the end of each treatment period. In addition, for those patients who discontinued, the summary will be broken down by primary reason for study discontinuation.

The number and percentage of patients who took the rescue medication and hence discontinued at week 24 will be presented. For each protocol deviation (PD), the number and percentage of patients for whom the PD applies will be tabulated.

### **2.3.2 Demographics and other baseline characteristics**

The following common background, demographics and baseline characteristics data will be analyzed as described below:

Continuous variables:

- Age (which is derived from date of birth and the screening assessment date)
- Height
- Weight
- Body mass index (BMI) = (body weight in kilograms) / (height in meters)

Categorical variables:

- Age categories (<65 years, 65 – 74 years, 75 years and older)
- Gender
- Race
- Source of patient referral

The following disease specific baseline characteristics and history of disease will be summarized as well:

- CASPAR, [REDACTED]
- Smoking status at baseline
- Disease background fo PsA/ axSpA, including time since diagnosis, etc
- Previous PsA/axSpA therapies
- PsA/axSpA functional status
- History of extra-axial involvement (uveitis, psoriasis, inflammatory bowel disease, dactylitis, enthesitis, peripheral arthritis)
- Time since onset of inflammatory back pain
- Number and proportions of previous DMARDs used

Unless otherwise specified, summary statistics will be presented for continuous variables for each treatment group and for all patients (total) in the randomized set. The number and percentage of patients in each category will be presented for categorical variables for each treatment group and all patients (total) in the randomized set.

### **2.3.3 Medical history**

Any condition entered on the Relevant medical history / current medical conditions CRF will be coded using the MedDRA dictionary. They will be summarized by system organ class (SOC) and preferred term (PT) of the MedDRA dictionary.

Summaries for cardiovascular medical history and psoriasis and psoriatic arthritis history will be provided as well.

Smoking history will be summarized by treatment group.

Unless otherwise specified, analyses will be based on the randomized set.

## **2.4 Treatments (study treatment, rescue medication, concomitant therapies, compliance)**

### **2.4.1 Study treatment / compliance**

#### **Study Treatment**

The analysis of study treatment data will be based on the safety set. The number of active and placebo injections will be summarized by treatment group.

#### **Duration of exposure**

The duration of exposure to study treatment will be summarized by treatment group.

In addition, the number and percentage of patients with cumulative exposure levels (e.g. any exposure,  $\geq 1$  week,  $\geq 2$  weeks,  $\geq 3$  weeks,  $\geq 4$  weeks,  $\geq 8$  weeks, etc.) will be presented.

Duration of exposure will be defined as the time from first dose of study treatment to the time of treatment switch (for patients who switch treatment) or end of treatment period (whichever is first). For patients who discontinue, this will be the subject's last visit in the corresponding treatment period.

Duration of exposure (years) = duration of exposure (days) / 365.25

Duration of exposure (100 subject years) = duration of exposure (years) / 100

The analyses of duration of exposure described above will be done for both the study treatment periods.

**Compliance** will be calculated based on documented study drug administrations and syringe counts and displayed by treatment group.

Compliance is expected to be 100%, unless temporary interruption is needed for safety reasons. Compliance will also be assessed by a Novartis monitor using information provided by the authorized site personnel.

#### **2.4.2 Prior, concomitant and post therapies**

Concomitant medications and significant non-drug therapies prior to and after enrolling into the study will be summarized by preferred term and ATC class of the World Health Organization (WHO) Drug Reference List.

Concomitant or prior medications entered into the database will be coded using the WHO Drug Reference List. Medical history/current medical conditions and AEs will be coded using MedDRA terminology.

#### **Prior and concomitant therapies**

Prior and concomitant medications will be summarized in separate tables by treatment group. Prior medications are defined as treatments taken and stopped prior to first dose of study treatment. Any medication given at least once between the day of first dose of randomized study treatment and the date of the last study visit will be a concomitant medication, including those which were started pre-baseline and continued into the period where study treatment is administered.

Medications will be presented in alphabetical order, by Anatomical Therapeutic Classification (ATC) codes and grouped by anatomical main group. Tables will show the overall number and percentage of patients receiving at least one treatment of a particular ATC code and at least one treatment in a particular anatomical main group.

Significant prior and concomitant surgeries and procedures will be summarized by primary system organ class and MedDRA preferred term.

The number and percentage of patients receiving prior and concomitant psoriatic arthritis therapy will be presented by randomized treatment group as well as the reasons for stopping their therapies (primary lack of efficacy, secondary lack of efficacy, lack of tolerability, other) and the total duration of exposure to psoriatic arthritis therapies previously.

Prior or concomitant medication will be identified by comparing recorded or imputed start and end dates of medication taken to the reference start date.

## Rescue medication

Rescue medication is defined as medication used to control symptoms that are not adequately controlled on study treatment.

No patient will be restricted from receiving necessary rescue medications for lack of benefit or worsening of disease, if rescue with prohibited treatments occurs prior to completion of Week 24 assessments, patients will be discontinued from the study.

Rescue medication will be summarized similarly to concomitant medication.

## 2.5 Analysis of the primary objective

The primary objective is to demonstrate that the efficacy of secukinumab is superior to placebo based on the percentage of patients with resolution of Achilles tendon enthesitis as assessed by the respective subcomponent of the Leeds enthesitis index (LEI) at 24 weeks in patients with active PsA and axSpA.

### 2.5.1 Primary endpoint

The primary endpoint is the percentage of patients with resolution of Achilles tendon enthesitis as assessed by the respective subcomponent of the LEI at Week 24. This resolution is referred to as 'response' below.

The analysis of the primary efficacy variable will be based on the FAS.

### 2.5.2 Statistical hypothesis, model, and method of analysis

The null hypothesis to be rejected is that the odds of response Week 24 are equal in both treatment groups. The corresponding alternative hypothesis is that the odds of response at Week 24 are higher under secukinumab compared to placebo.

In other words: Let  $p_j$  denote the proportion of responders at Week 24 for treatment group  $j$ ,  $j=0, 1$ , where

- 0 corresponds to placebo
- 1 corresponds to secukinumab

The following hypotheses will be tested:

$H_0: (p_1 / (1-p_1)) / (p_0 / (1-p_0)) = 1$  versus  $H_1: (p_1 / (1-p_1)) / (p_0 / (1-p_0)) \neq 1$

In other words,  $H_1$ : The odds ratio of achieving a response at Week 24 for secukinumab vs Placebo is different from 1.

The hypotheses can also be re-written as a difference of proportions as follows:

In statistical terms,  $H_0: p_1 = p_0$ ,  $H_1: p_1 \neq p_0$ , i.e.

$H_1$ : The difference of proportions at Week 24 for secukinumab vs Placebo is different from 0.

The primary analysis will be performed comparing treatments with respect to the primary efficacy variable in a logistic regression model with the factors treatment, country and

[figure not shown]
stratification factor diagnosis (PsA or axSpA). The odds ratio and its 95% confidence interval (CI) and p-value will be presented comparing secukinumab to placebo at Week 24.

The study is said to be positive/declared as success if the lower limit of 95% CI of odds ratio is greater than 1.

The primary endpoint (percentage of patients with resolution of Achilles tendon enthesitis) will additionally be analyzed separately for the subgroups of patients with PsA or axSpA, using the same model as for the respective pooled, overall population tests (except for the stratification factor). Those two subgroup analyses are included in the confirmatory testing strategy. The primary model will also be recalculated with the stratification factor included as well as with respective term for a strata\*treatment interaction.

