	 Physician's global assessment of heel enthesiopathy activity (VAS).
	 Patient's global assessment of heel enthesiopathy activity (VAS). Magnetic Resonance Imaging (MRI) including subcomponents of the Psoriatic arthritis magnetic resonance imaging scoring system (PsAMRIS).
Key safety assessments	Evaluation of adverse events (AEs)/serious adverse events (SAEs).
	Physical examination.
	Vital signs.
	Height and weight.

	 QuantiFERON TB-Gold test. Laboratory evaluations (Hematology, Clinical Chemistry, Urinalysis). Electrocardiogram (ECG). Pregnancy and assessment of fertility. Tolerability of secukinumab.
Other assessments	 Medical outcome short form (36) health survey (SF-36 v2). Human leukocyte antigen B27 (HLA-B27)
Data analysis	The primary endpoint, the resolution of Achilles tendon enthesitis at 24 weeks will be analyzed using a logistic regression model with the factors treatment, $TNF\alpha$ inhibitor status and stratification factor diagnosis (PsA or axSpA).
Key words	Active psoriatic arthritis, axial spondyloarthritides, subcutaneous, secukinumab in prefilled syringe, enthesitis, achilles tendon

1 Introduction

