9.4.2 Statistical model, hypothesis, and method of analysis

The null hypothesis to be rejected is that the odds of response Week 24 are equal in both treatment groups. The corresponding alternative hypothesis is that the odds of response at Week 24 are higher under secukinumab compared to placebo.

Let pj denote the proportion of responders at Week 24 for treatment group j, j=0, 1, where

- 0 corresponds to placebo
- 1 corresponds to secukinumab

The following hypotheses will be tested:

H0: (p1 / (1 - p1)) / (p0 / (1 - p0)) = 1 versus HA: $(p1 / (1 - p1)) / (p0 / (1 - p0)) \neq 1$

In other words:

HA: The odds ratio of achieving a response at Week 24 for secukinumab vs Placebo is different from 1.

The primary analysis will be performed comparing treatments with respect to the primary efficacy variable in a logistic regression model with the factors treatment, $TNF\alpha$ inhibitor status and stratification factor diagnosis (PsA or axSpA). The odds ratio and its 95% confidence interval and p-value will be given.

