## 5.4 Statistical models

### 5.4.1 Primary analysis

The primary analysis will be performed comparing treatments with respect to the primary efficacy variable in a logistic regression model with the factors treatment, country and stratification factor diagnosis (PsA or axSpA).

```
Proc logistic data=aaa;  
Class TRT COUNTRY STRATA / param=glm;  
Model AVAL = TRT COUNTRY STRATA;  
Lsmeans TRT / diff cl exp;  
Ods output diffs=lsm_diff;  
Run;
```

In cases where separation is a concern for the primary endpoint at Week 24, e.g. 0% or 100% response in one treatment (sub)group, an exact logistic regression model will be applied to all visits. To ensure convergence, this model will not include any continuous covariates.

SAS Code for Logistic model:

```
Proc logistic data=aaa exactonly;  
Class TRT STRATA / param=glm;  
Model AVAL = TRT STRATA;  
Exact TRT / estimate=both;  
Ods output exactoddsratio=exactoddsratio;  
Run;
```

For subgroup analysis, the above code will be used for each stratification factor.

The primary model will also be recalculated with the above factors included as well as with respective terms for a subgroup\*treatment interaction.

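### The protocol and the SAP give the primary logistic model different covariates: TNFα-inhibitor status in the protocol, country in the SAP

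*SAP*

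**What the plan says.** Protocol 9.4.2 specifies a logistic regression for the primary endpoint with treatment, TNFα "inhibitor status and stratification factor diagnosis (PsA or axSpA") as factors. The data-analysis entry of the protocol summary agrees: "the resolution of Achilles tendon enthesitis at 24 weeks will be analyzed using a logistic regression model with the factors treatment", followed by TNFα-inhibitor status and diagnosis.

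SAP 2.5.2 specifies the primary "efficacy variable in a logistic regression model with the factors treatment, country and" the diagnosis stratum. The code in SAP 5.4.1 reads "Model AVAL = TRT COUNTRY STRATA". TNFα-inhibitor status appears in no visible SAP model.

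The SAP introduction says that data will be analysed "according to the data analysis section 9 of the clinical study protocol" and that "any deviations from the protocol are documented". SAP section 4, which should list changes to protocol-specified analyses, is marked as not applicable.

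The decision rule is in SAP 2.5.2: "The study is said to be positive/declared as success if the lower limit of 95% CI of odds ratio is greater than 1". The confirmatory PsA and axSpA tests follow, "using the same model as for the respective pooled, overall population tests (except for the stratification factor").

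**The concern.** These are two different models, and no rule says which one prevails. The SAP's general statement points to the protocol model; its explicit text and code point to the other. The odds ratio and confidence interval that decide the trial can come from either.

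The conflict reaches further than the overall test. The PsA and axSpA tests, which are confirmatory once the overall test succeeds, reuse the primary model without the diagnosis factor. The bone marrow oedema endpoint inherits the conflict as well, although it is exploratory.

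Timing makes it matter. Under protocol 5.4 the sponsor is unblinded after the Week 24 database lock. A choice between the models made after that point cannot be shown to be independent of the results.

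**Working it through.** **Texts side by side**

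| Item | Protocol | SAP |
|---|---|---|
| Primary model | 9.4.2 and summary: treatment, TNFα-inhibitor status, diagnosis | 2.5.2 and 5.4.1: treatment, country, diagnosis |
| PsA and axSpA tests | 9.5.1.6: same model as overall | 2.5.2: same model without diagnosis |
| Bone marrow oedema | 9.5.1.2: analogous to primary | 2.7.2: treatment, country, diagnosis |
| Heel pain ANCOVA | 9.5.1.1: includes country | 2.7.2: includes country |
| Fallback under separation | none given | 5.4.1: exact model, treatment and diagnosis only |

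With a two-level TNF factor the protocol model has 4 parameters: intercept, treatment, TNF status and diagnosis. With K countries the SAP model has 3 + (K − 1) = K + 2, so 7, 12 or 17 for K = 5, 10 or 15. The documents do not give K.

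**Likely cause (inference).** The SAP history shows one version, dated 23-Jun-2016. SAP 1.1 has an 8-week screening period, where the protocol summary has 10. SAP Table 5.1-4 still codes prior TNF-inhibitor use (INCL16, EXCL09) and heel pain beyond 5 years (INCL06) as deviations. Amendment 3 admitted TNF-exposed patients and removed the 5-year limit.

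**The plan's own figure.** Protocol 9.8 gives 89 per arm for 45% versus 21%, two-sided 5%, 90% power. The pooled formula is n = [z₀.₉₇₅√(2p̄q̄) + z₀.₉₀√(p₁q₁ + p₀q₀)]² / (p₁ − p₀)², with p̄ = 0.33. This gives (1.960 × 0.665 + 1.282 × 0.643)² / 0.0576 ≈ 78.6, so 79 per arm, or 87 with continuity correction, within 2 patients of 89. The calculation contains no covariate, so it cannot show which model was intended.

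**How often the choice would matter.**
- From the documents: 200 patients, half PsA and half axSpA, 1:1 allocation; success if the lower 95% limit of the odds ratio exceeds 1; a subgroup success counts only after overall success under the same model.
- Assumed: TNF-exposed share 20% or 40% (40% is the protocol's planned TNF-IR cap), TNF odds ratio 0.5 or 1.0, country log-odds SD 0 or 0.5, and 5, 10 or 15 countries.
- Fifteen settings were run, with 10,000 trials each. Both models were fitted to the same data. Monte Carlo error is at most √(0.25/10,000) = 0.5 points.

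| True rates | Overall verdict differs | Each gated subgroup verdict differs | At least one of three differs |
|---|---|---|---|
| 45% vs 21% (design) | 1.4–2.7% | 6.5–11.9% | 13.2–23.7% |
| 42.2% vs 21.5% (150 mg and placebo rates in 9.8) | 2.7–5.4% | 7.3–13.5% | 15.5–27.4% |
| 21% vs 21% (no effect) | 0.9–1.6% | 0.4–0.7% | not tabulated |

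Overall power is 95–96% at the design rates and 88–90% at 42.2% versus 21.5%, under either model. With no effect, false success is 2.2–2.7% (TNF model) and 2.4–3.0% (country model), against a nominal 2.5%.

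As a check on the simulation, the unadjusted formula at 100 per arm gives Φ[(0.24 × √100 − 1.303)/0.643] = 95.6%. At 50 per arm it gives 73.0%, against simulated gated subgroup power of 72–74% (TNF model) and 70–74% (country model). A smaller simulation with other assumed inputs (30% exposed, TNF log odds ratio −0.6, country SD 0.4, 5 or 10 countries, 2,000 trials each) gave overall disagreement of 2.25% and 3.0% at 45% versus 21%.

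**The case against.** The strongest reply is that little changes in practice. Both models keep treatment and the only stratification factor, power and type I error are nearly equal, and the overall verdict rarely differs. The SAP's reference to protocol section 9 arguably names the governing text. This stands as to size, and it is why the point is about pre-specification and not operating characteristics. It does not settle which model is run, because the SAP's code contradicts that reference.

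A second reply is that the figure for at least one of three verdicts leans on two subgroup tests that the documents rate at only about 58% (protocol) or 46% (SAP) power, and on an assumed number of countries. Both are true. It also notes that SAP 5.4.1 switches to an exact model without country when separation is a concern. With 10 countries, about 80–84% of simulated subgroups of 100 contained a country with all or no responders; with 15, 97–99%; with 5, 20–25%. Whether that triggers the fallback is unclear from the SAP. When the fallback was applied in every such case, at least one verdict still differed in 16–18% of trials, inside the range above.

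Third, the account of an outdated SAP is undated inference. One row, INCL03B, already uses a one-joint threshold, which may not fit it. If the account is right, the entry in section 4 was correct when written and is not a false declaration. SAP 2.14 allows an additional Week 24 SAP, but only if required.

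Finally, one SAP section is redacted. It may hold the TNF-status subgroup analysis of protocol 9.5.1.6, so that analysis cannot be called missing. It would not alter the visible primary model or code.

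**Conclusion.** The concern holds. The current protocol and the SAP name different primary models, and the SAP records no departure. At the design rates the effect on the overall verdict is small (1.4–2.7% of trials), and it is larger across the three confirmatory verdicts (13.2–23.7%). Those sizes depend on assumed TNF effects, country variation and number of countries. The textual contradiction depends on none of them. A confirmatory test needs one model fixed before unblinding, so this should be resolved before the Week 24 lock.

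**What to change.** Issue one SAP amendment before the Week 24 database lock:

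1. In SAP 2.5.2 and 5.4.1, and in the bone marrow oedema model, replace country with TNFα-inhibitor status. Alternatively, amend the protocol so that both documents name the same model.
2. Define the levels of TNFα-inhibitor status, which the protocol leaves open. Inclusion criterion 16 requires every TNF-exposed patient to be an inadequate responder or intolerant, so in eligible patients exposed and TNF-IR coincide and two levels suffice. State how to code ineligible patients who remain in the FAS.
3. Run the PsA and axSpA tests with the same model without diagnosis.
4. State what triggers the exact-logistic fallback and which factors it keeps. State the covariates for the LEI resolution model deliberately, since the protocol gives it no explicit model.
5. Add the TNF-status subgroup analysis if the redacted section does not contain it.
6. Update INCL06, INCL16 and EXCL09 to the current eligibility criteria. This affects tabulation only, since all three are coded for inclusion in every analysis set.
7. Record the alignment in the document history and list any remaining departure in section 4.

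No new data are needed: protocol 6.2 already collects previous PsA/axSpA therapies.
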